10.6.6.1 Starting Dose, Dose Escalation Scheme and Stopping Criteria10.6.6.1.1 Starting Dose

The initial dose level of 300 mg is based upon findings from the 3-month GLP toxicology study in cynomolgus monkeys and predictions around GDF15 suppression (see Section 10.4.2). The first participant in Cohort 1 must complete 1 week on study post the AZD8853 administration (Cycle 1 Day 1) without any DLTs before additional participants may be enrolled into the first cohort. A waiting period between additional participants in the cohort is not required.

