6.2.3 Treatment Administration

No premedication for the prevention of IRRs prior to the first infusion of AZD8853 is permitted (ie, primary prophylaxis). Any planned premedication with acetaminophen (paracetamol), histamine (H1 and H2)-receptor antagonists, with subsequent infusions of AZD8853 following an IRR (ie, secondary prophylaxis) is permitted. Steroids should not be used as routine premedication for Grade 1 or 2 IRRs. If more than one participant during the course of the study develops a Grade ≥ 3 IRR during the first infusion, the SRC may recommend premedication for all subsequent participants to be implemented for the first infusion as follows: paracetamol/acetaminophen (500 to 1000 mg orally) and diphenhydramine (25 to 50 mg orally or i.v.; or an alternative antihistamine at an adequate dose), should be administered approximately 30 minutes prior to infusion with AZD8853. For additional premedication guidelines for the prevention of IRR, refer to Section 6.5.

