10.6.6.1.3 Escalation Cohorts

Dose escalation will follow the mTPI-2 algorithm (Guo et al, 2017) as described below. Dose escalation cohorts will initially enrol 3 to 5 participants per cohort (to ensure at least 3 evaluable participants for dose-escalation decisions). A minimum of 3 participants must complete the DLT-evaluation period before making an escalation decision. A maximum of 9 participants may be enrolled in each dose-escalation cohort.

- 1. The MTD will be determined based on assessment of DLT according to the mTPI-2 algorithm (see Table 16).
- 2. A minimum of 3 DLT-evaluable participants are required in each dose level unless unacceptable toxicity is encountered in the first 2 participants prior to enrolment of the third participant, which would require dose de-escalation per the mTPI-2 design. For a dose level that has fewer than 3 participants who are DLT-evaluable, participants will be replaced.
- 3. If a de-escalation decision is made, choice of de-escalation to the previous main dose level or an intermediate dose level below will be at the discretion of the SRC. In the eventuality that a decision is made to de-escalate back to a dose escalation level that was previously deemed safe, in which additional participants (Part B1) have since been enrolled at that dose level, these participants will now be included in further dose-escalation decisions following mTPI-2 rules.
- 4. If a stay ("S") decision is made, additional participants will be enrolled up to a maximum of 9 participants for a given dose level (typically in groups of 2 to 4 participants).
- 5. After the sentinel dosing of the first participant in the initial cohort, participants 2 and 3 dosing will be staggered such that administration of the first dose is separated by at least 48-hours before the next participant is dosed. In subsequent cohorts, a 48-hour separation in first dosing between participants is required for the first 3 participants in each cohort. Provided there are no serious or unexplained safety issues after the first 3 participants, as determined by the respective treating physician, participants may be enrolled concurrently or sequentially for the remainder of the cohort with the Sponsor's agreement. Intra-participant dose escalation will not be allowed.

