##### 3.3.7.1 Dose escalation: mTPI-2

###### Part A: Substudy 1

The Modified Toxicity Probability Interval-2 (mTPI-2) employs a simple beta-binomial Bayesian model (Guo et al 2017). The posterior density of the toxicity probability is divided into multiple intervals with equal length. These intervals are categorized as underdosing (below), proper dosing (equivalent), and overdosing (above) in terms of target toxicity. The underdosing interval corresponds to a dose escalation, overdosing corresponds to a dose de-escalation, and proper dosing corresponds to staying at the current dose. The design for the dose-escalation phase of the study uses a target Dose Limiting Toxicity (DLT) rate of **[REDACTED]**% and an equivalence interval **[REDACTED]** for dose-escalation/de-escalation decisions as well as MTD determination. A dose level is considered unsafe, with no additional participants enrolled at that dose level, if it has an estimated 95% or more probability of exceeding the target DLT rate of **[REDACTED]**% (i.e.,  $P [DLT > [REDACTED]\% | \text{data}] \geq 95\%$ ).

For specific dose escalation rules, refer to CSP Section 10.6.6.1.3.

For dose escalation (Part A) cohorts of at least 3 and up to 9 evaluable participants are required for each dose cohort (unless unacceptable toxicity is seen before 3 evaluable participants). The total number of participants will depend on the number of non-evaluable participants and the number of dose escalations necessary in order to declare MTD/RP2D. More patients may also need to be enrolled to a dose level if toxicity is observed. It is anticipated that approximately up to 5 dose-escalation cohorts of up to 9 evaluable participants may be included resulting in an overall total of up to approximately 45 participants.

The dosing cohorts are grouped depending on the starting dose they are planned. The starting dose for this study is 300 mg with the maximum dose set at 3000 mg.

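### The Starting Dose section waives any gap between later Cohort 1 participants, while the escalation rules require at least 48 hours between the first doses of participants 2 and 3

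*Protocol*

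**What the plan says.** Two places in the protocol govern the timing of first doses in Cohort 1.

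- **Section 10.6.6.1.1 (Starting Dose).** It sets the sentinel rule: "The first participant in Cohort 1 must complete 1 week on study post the AZD8853 administration (Cycle 1 Day 1) without any DLTs". Nobody else may join the cohort until that is done. Its closing sentence is: "A waiting period between additional participants in the cohort is not required". It gives no exception and does not refer to the escalation rules.
- **Section 10.6.6.1.3 (Escalation Cohorts), item 5.** It starts from the same point, "After the sentinel dosing of the first participant in the initial cohort", and its rule for that cohort is: "participants 2 and 3 dosing will be staggered such that administration of the first dose is separated by at least 48-hours". For later cohorts it says: "In subsequent cohorts, a 48-hour separation in first dosing between participants is required for the first 3 participants in each cohort". Only then does it relax. "Provided there are no serious or unexplained safety issues after the first 3 participants", as judged by the treating physician, and with the Sponsor's agreement, the rest of the cohort may be enrolled concurrently or one after another.

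The SAP adds no timing rule of its own. Section 3.3.7.1 says: "For specific dose escalation rules, refer to CSP Section 10.6.6.1.3". Protocol Section 6.2.3 is relevant background: "No premedication for the prevention of IRRs prior to the first infusion of AZD8853 is permitted".

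**The concern.** For participants 2 and 3 of the first cohort, one section says no wait is needed and the other demands at least 48 hours. Neither refers to the other, and the protocol does not say which prevails.

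This is the first administration of AZD8853 to humans, and Section 2.3.1 states that no clinical data are available. With primary prophylaxis against infusion reactions ruled out, spacing the first doses is one of the safeguards against several participants having an acute reaction at once. Item 2 of Section 10.6.6.1.3 also provides for de-escalation when unacceptable toxicity appears in the first two participants before a third is enrolled. If participants 2 and 3 are dosed together, a reaction in participant 2 cannot spare participant 3.

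There is a lesser consequence for the analysis. SAP Section 3.3.5 lists dosing not given per protocol among possible important protocol deviations. With two protocol statements pointing different ways, it becomes arguable whether dosing participants 2 and 3 on the same day is a deviation.

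**Working it through.** The plan states no figure to reproduce. The check sets the two rules side by side and works out the earliest permitted first-dose times.

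**Inputs**

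- Sentinel hold in Cohort 1: 1 week = 7 × 24 = 168 h (10.6.6.1.1).
- Gap between later Cohort 1 participants: none required (10.6.6.1.1).
- Gap between participants 2 and 3 of Cohort 1: at least 48 h (10.6.6.1.3, item 5).
- Gap between the first three participants of later cohorts: 48 h (item 5).
- Initial cohort size: 3 to 5 (10.6.6.1.3), so the additional participants number 2 to 4.

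**Earliest first dose, in hours after participant 1**

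| Rule applied | Participant 2 | Participant 3 | Minimum gap, 2 to 3 |
|---|---|---|---|
| Cohort 1, item 5 | 168 | 168 + 48 = 216 | 48 |
| Cohort 1, 10.6.6.1.1 read alone | 168 | 168 | 0 |
| Later cohorts, item 5 | 48 | 48 + 48 = 96 | 48 |

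With participant 1 dosed on Day 1, participants 2 and 3 could both be dosed on Day 8 under 10.6.6.1.1 alone. Under item 5, participant 3 could not be dosed before Day 10.

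The hour counts assume that a participant can be dosed as soon as the sentinel hold on enrolment ends. If screening has to follow the hold, the times for participants 2 and 3 both move later. The required gap between them is still 0 h under one section and at least 48 h under the other.

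**Participants 4 and 5.** Item 5 sets no fixed interval for them, so the two sections do not conflict on time. The Starting Dose sentence does pass over item 5's two conditions: no serious or unexplained safety issue in the first three, and the Sponsor's agreement.

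**The case against.** The strongest reply is that the sentence in 10.6.6.1.1 follows directly on the one-week hold and may mean only that this hold is not repeated for each new participant. It may also concern enrolment, which Table 11 defines as signing the consent form, whereas item 5 concerns first dosing. On either reading both sections can be obeyed, since saying that a wait is not required does not direct anyone to dose simultaneously. Item 5 also sits under the same parent heading, close by, and explicitly picks up after the sentinel. Spacing is not the only protection either: Section 6.2.4 requires monitoring during and after infusion and immediate access to treatment for anaphylaxis, and Section 6.2.3 lets the SRC recommend premedication if more than one participant has a Grade 3 or worse reaction during the first infusion.

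Much of this stands. The 48-hour rule exists and is mandatory, and a site that follows item 5 breaches nothing. For participants 4 onward the Starting Dose section omits conditions but does not contradict a time rule. The SAP reference directs the analyst to item 5 without setting precedence for sites.

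The softer reading does not remove the problem, because the sentence does not state it. The waiting period it waives is unrestricted. The split between enrolment and dosing is not kept either, since item 5 itself speaks of enrolment when it lifts the dosing stagger. The other protections help manage a reaction once it occurs, but they do not stop two participants from being exposed at the same time.

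**Conclusion.** The concern holds. As written, 10.6.6.1.1 omits the 48-hour first-dose stagger that item 5 makes mandatory for participants 2 and 3 of Cohort 1, and it appears to negate it. Read alone, it would permit simultaneous dosing of those two participants.

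The size is limited to one interval in one cohort, with the required gap falling from at least 48 h to 0 h. The one-week sentinel period is intact, and it is longer than the 48 h between participants 1 and 2 in later cohorts. Those cohorts, every endpoint and every mTPI-2 decision are unchanged. The practical risk arises only if a site relies on the Starting Dose section without the escalation rules.

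The documents do not say whether Cohort 1 dosing is complete. If it is, the remaining value of a correction is a clear rule for judging what was done. Because this is a first-in-human dosing instruction and one sentence corrects it, it should be fixed.

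**What to change.** Keep item 5 as it is. Replace the last sentence of Section 10.6.6.1.1 with:

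*After the 1-week sentinel period, first doses of participants 2 and 3 will be separated by at least 48 hours; subsequent participants in the cohort follow Section 10.6.6.1.3, item 5.*

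If the sponsor meant only that the one-week hold is not repeated, this wording is consistent with that intention and removes the ambiguity.

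The cost is one sentence in a protocol amendment or addendum. The added time in Cohort 1 is at most 216 − 168 = 48 h, or 2 days, which item 5 already imposes. No analysis, sample size or SAP text needs to change.

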10.6.6.1.2 Safety Review Committee

Please refer to Section 9.6 for details on the SRC.

10.6.6.1.3 Escalation Cohorts

Dose escalation will follow the mTPI-2 algorithm (Guo et al, 2017) as described below. Dose escalation cohorts will initially enrol 3 to 5 participants per cohort (to ensure at least 3 evaluable participants for dose-escalation decisions). A minimum of 3 participants must complete the DLT-evaluation period before making an escalation decision. A maximum of 9 participants may be enrolled in each dose-escalation cohort.

- 1. The MTD will be determined based on assessment of DLT according to the mTPI-2 algorithm (see Table 16).
- 2. A minimum of 3 DLT-evaluable participants are required in each dose level unless unacceptable toxicity is encountered in the first 2 participants prior to enrolment of the third participant, which would require dose de-escalation per the mTPI-2 design. For a dose level that has fewer than 3 participants who are DLT-evaluable, participants will be replaced.
- 3. If a de-escalation decision is made, choice of de-escalation to the previous main dose level or an intermediate dose level below will be at the discretion of the SRC. In the eventuality that a decision is made to de-escalate back to a dose escalation level that was previously deemed safe, in which additional participants (Part B1) have since been enrolled at that dose level, these participants will now be included in further dose-escalation decisions following mTPI-2 rules.
- 4. If a stay ("S") decision is made, additional participants will be enrolled up to a maximum of 9 participants for a given dose level (typically in groups of 2 to 4 participants).
- 5. After the sentinel dosing of the first participant in the initial cohort, participants 2 and 3 dosing will be staggered such that administration of the first dose is separated by at least 48-hours before the next participant is dosed. In subsequent cohorts, a 48-hour separation in first dosing between participants is required for the first 3 participants in each cohort. Provided there are no serious or unexplained safety issues after the first 3 participants, as determined by the respective treating physician, participants may be enrolled concurrently or sequentially for the remainder of the cohort with the Sponsor's agreement. Intra-participant dose escalation will not be allowed.
- 6. At the discretion of the Sponsor, dose escalation may be stopped before an MTD is reached. In this case, the doses for evaluation in the dose-expansion parts (Part B and Part C) may be chosen based on an assessment of available PK, PD, safety, or efficacy data.
- 7. The MTD will be determined by isotonic regression analysis applied to DLT rates observed during dose escalation using the mTPI-2 method (Guo et al, 2017).

The mTPI-2 employs a simple beta-binomial Bayesian model. Decision rules are based on calculating the UPM of three intervals corresponding to underdosing, proper dosing, and overdosing in terms of toxicity. The underdosing interval corresponds to a dose escalation, overdosing interval corresponds to a dose de-escalation, and proper dosing interval corresponds to staying at the current dose. Given an interval and a probability distribution, the UPM of that interval is defined as the probability of the interval divided by the length of the interval. The mTPI-2 design calculates the UPMs for the multiple equal toxicity intervals, and the one with the largest UPM implies the corresponding dose-finding decision. The design for the dose-escalation part of the Substudy 1 uses a target DLT rate of % and an equivalence interval of (%, %) for dose-escalation/de-escalation decisions as well as MTD determination. A dose level will be considered unsafe, with no additional participants enrolled at that dose level, if it has an estimated 95% or more probability of exceeding the target DLT rate of (ie, P [DLT > 60 % data] > 95%) with at least 3 DLT-evaluable participants treated and evaluated at that dose level. In Table 16 dose escalation/de-escalation decision rules are computed based on the above information.

Dose-escalation decisions guided by the mTPI-2 design with the targeted DLT rate p_T and the equivalence interval (EI) = p_T . The table lists the decisions for up to 9 participants treated at a given dose. The column in this table represents the number of participants enrolled at the dose, and the row represents the number of DLTs at the same dose. The dose-escalation decisions are as follows: E: Escalate to the next higher dose; S: Stay at the current dose; D: De-escalate to the previous lower dose and marking the current dose and its higher doses as unacceptably toxic so that they will never be used again in the remainder of the trial.

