Dose escalation will follow the modified toxicity probability interval (mTPI-2) algorithm and will be based on the dose limiting toxicity (DLT) evaluable population (all enrolled participants who complete the DLT evaluation period of 21 days after receiving at least 75% of the first infusion of study intervention, or who experience any DLT). Safety and tolerability will be assessed in terms of DLTs, adverse events (AEs), serious AEs (SAEs), vital signs,

clinical chemistry/haematology parameters, dose interruptions/discontinuations, and electrocardiogram (ECG) data. These variables will be collected for all participants. All safety analyses will be performed on the Safety Population (all participants who receive at least one dose of study intervention) and will be summarised using descriptive statistics. Adverse events will be coded using the latest version of Medical Dictionary for Regulatory Activities (MedDRA) and graded according to National Cancer Institute Common Terminology Criteria for Adverse Events (NCI CTCAE) v5.0.

Efficacy

The efficacy endpoints for tumour response (objective response rate [ORR], disease control rate [DCR] at 15 weeks, duration of response [DoR], and percentage change in tumour size) will be summarised for the Response Evaluable Population (all dosed participants who have measurable disease at baseline) using Response Evaluation Criteria in Solid Tumours (RECIST) v1.1 by Investigator assessment. The efficacy endpoints of progression-free survival (PFS) and overall survival (OS) will be summarised based on the Safety Population.

The RECIST tumour response data will be used to programmatically determine each participant's visit response and to derive the endpoints of ORR, DoR, DCR at 15 weeks, percentage change in tumour size, and PFS. Endpoints will be summarised using descriptive statistics and Kaplan Meier methods as appropriate.

Additionally, the percentage change in circulating tumour deoxyribonucleic acid (ctDNA) from pre-treatment (baseline) to each post baseline timepoint as well as the maximum change will be summarised using descriptive statistics on the Safety Population.

Pharmacokinetics

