3 OBJECTIVES AND ENDPOINTS

Table 4 Objectives and Endpoints

Please see the study-specific objectives and endpoints for each Substudy within the respective Substudy section. The following objectives are applicable for all Substudies.

Type	Objectives	Endpoints	
Primary			
Safety	To assess safety and tolerability, characterise DLTs (in dose escalation parts only) and determine the MTD or RP2D of AZD8853 in participants with selected advanced/metastatic solid tumours in each Substudy	 Incidence of AEs and SAEs Incidence of DLTs in dose escalation parts only Incidence of clinically significant changes from baseline in clinical laboratory parameters, vital signs, and ECG results Incidence of AEs leading to discontinuation of AZD8853 	
	Secondary		
Efficacy	To determine the preliminary anti-tumour activity of AZD8853 in participants with selected advanced/metastatic solid tumours in each Substudy To assess the efficacy of AZD8853 using longitudinal blood samples in participants with selected advanced/metastatic solid tumours in each Substudy	According to RECIST v1.1 ORR, DCR at Week 15, DoR, and PFS Change in target lesion tumour size from baseline OS Change in ctDNA from baseline levels between baseline and post-treatment timepoints	
PK	To determine the PK of AZD8853 in serum when administered in participants with selected advanced/metastatic solid tumours in each Substudy	PK parameters to be evaluated include but not limited to Cmax and AUC	
Immunogenicity	To assess the immunogenicity of AZD8853 in participants with selected advanced/metastatic solid tumours in each Substudy	Number and percentage of participants who develop detectable ADAs against AZD8853 in serum samples	

Abbreviations: ADA = antidrug antibodies; AE = adverse event; AUC = area under the concentration time curve; Cmax = maximum observed concentration; ctDNA = circulating tumour deoxyribonucleic acid; DCR = disease control rate; DLT = dose limiting toxicity; DoR = duration of response; ECG = electrocardiogram; MTD = maximum tolerated dose; ORR = objective response rate; OS = overall survival; PD = pharmacodynamic(s); PFS = progression free survival; PK = pharmacokinetic(s); RECIST = response evaluation criteria in solid tumours; RP2D = recommended Phase 2 dose; SAE = serious adverse event.

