9.4.2 Safety Analyses

Safety and tolerability will be assessed in terms of DLTs, AEs/SAEs, ECOG status, vital signs, clinical chemistry/haematology parameters, dose interruptions/discontinuations and ECG data. These variables will be collected for all participants. All safety analyses will be performed on the Safety Population, except for the evaluation of DLTs that will be performed on the DLT Evaluable Population. Additional subgroup analysis of safety may be performed, as specified in the SAP.

Medical Dictionary for Regulatory Activities will be used to code AEs. Adverse events will be graded according to the NCI CTCAE v5.0. The number of participants in each dose cohort (Part A) and each expansion (Parts B and C) experiencing each AE will be summarised by MedDRA SOC and preferred term. The number and percentage of participants with AEs in

different categories (eg, causally related, CTCAE Grade \geq 3, etc) will be summarised by dose regimen; events in each category will be further summarised by MedDRA SOC and preferred term. Serious adverse events will be summarised separately, if a sufficient number occurs.

Adverse event summary tables will include only treatment-emergent AEs. Adverse events will be defined as treatment-emergent if they have an onset or worsen (by Investigator report of a change in intensity) during the study treatment or the safety follow-up period (defined as 90 days after last dose of study treatment) but prior to subsequent anti-cancer therapy. Adverse events occurring outside this period will only be listed.

During the evaluation of the AE data, an AstraZeneca medically qualified expert will review the list of AEs that were not reported as SAEs and AEs leading to discontinuation. Based on the expert's judgement, significant AEs of particular clinical importance may, after consultation with the Global Patient Safety Physician, be considered OAEs and reported as such in the CSR. A similar review of laboratory/vital signs (pulse and BP)/ECG data will be performed for identification of OAEs. Examples of these could be marked haematological and other laboratory abnormalities, and certain events that lead to intervention (other than those already classified as serious), dose reduction, or significant additional treatment.

Duration of exposure will be summarised.

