10.6.7 Dose Expansion

Part B

The 2 dose expansion levels will be chosen based on peripheral target engagement and non-overlapping PK in order to evaluate intra-tumoural PD activity and help determine the RP2D. One dose expansion level will be the MTD/HPDD and one dose expansion level will be lower than the MTD/HPDD. Each dose level will enrol approximately 20 participants with NSCLC or MSS-CRC (enrolling approximately 10 participants in each tumour type). Expansions may open either in parallel or sequentially at Sponsor's discretion. Expansions may start before the MTD/HPDD has been determined.

Part C

The two efficacy expansions will be determined based on emerging data from Part A and/or Part B and may include two indications at a single dose level or one indication at two dose levels. If the RP2D cannot be adequately determined from Part B and additional data (eg, efficacy) is required to guide RP2D determination, then two dose levels in one indication will be investigated. If the RP2D is determined at the end of Part B, RP2D will be evaluated in two indications. Each efficacy expansion will enrol up to approximately 40 participants which may include up to 10 participants from the relevant Part B expansion. An interim analysis will take place after 20 participants (further details in Section 10.9.5).

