10.6.8 Definition of DLT

Dose limiting toxicity includes event(s) which happen during the 21 days of Cycle 1 of Part A and represent ≥ Grade 3 toxicity, as defined below, which is not clearly attributable to the disease under investigation, other concomitant medications, disease-related processes under investigation, or another non-drug-related aetiology, with modifications or exceptions noted below.

The DLT evaluation period is from the first exposure of AZD8853 until the end of Cycle 1, which is 21 days. All DLTs must be documented as AEs, graded according to

NCI CTCAE v5.0 and need to be followed until improvement to CTCAE Grade < 1. A minimum of at least 3 DLT-evaluable participants are required for the SRC to hold a dose-escalation vote.

An AE not listed below, or an AE meeting the DLT criteria below but occurring outside of the DLT period may be defined as a DLT-like event after consultation with the Sponsor and Investigators based on the emerging safety profile.

The following toxicities constitute a DLT:

- Any death not clearly due to the underlying disease or extraneous causes.
- Grade 4 adverse events of immune nature (imAE).
- Any ≥ Grade 3 non-infectious pneumonitis regardless of duration; diagnosis should include clinical evaluation, monitoring of oxygenation using pulse oximetry (resting and exertion), laboratory workup and high-resolution CT scan.
- Any \geq Grade 3 non-infectious colitis irrespective of duration after confirmation by colonoscopy and histopathology.
- Any Grade 3 imAE, including rash, pruritus, or diarrhoea (NOTE: this excludes colitis or pneumonitis, as these AEs are already defined above), that does not downgrade to Grade ≤ 2 within 7 days after onset of the event despite maximal supportive care including systemic corticosteroids.
- Liver transaminase elevation:
 - i. Criteria for all participants except participants with elevated transaminases (ALT/AST) at baseline/screening due to liver metastasis:
 - Isolated liver transaminase elevation $> 5 \times \text{but} \le 8 \times \text{ULN}$ that does not downgrade to AST/ALT $\le 3 \times \text{ULN}$ within 14 days after onset with optimal medical management.
 - Isolated liver transaminase elevation > 8 × ULN regardless of duration or reversibility.

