10.6.10 Definition of DLT Evaluable Participant

For decisions on dose escalation, an evaluable participant is defined as a participant who has received AZD8853 and either:

 Has received at least 75% of the AZD8853 infusion and has completed safety evaluation requirements during the DLT evaluation period of 21 days in Cycle 1. Participants who do not remain in the study up to this time for reasons other than DLT will be considered non-evaluable for DLT assessment.

OR

• Has experienced a DLT during the DLT evaluation period.

Non-evaluable participants in the dose-escalation cohorts will be replaced in the same dose cohort if needed to ensure a minimum of 3 DLT-evaluable participants.

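### Part B1 participants can enter mTPI-2 decisions after a step back to their dose, but a DLT is defined only for Part A, so their toxicities cannot enter the count as worded

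*Protocol*

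**What the plan says.** Protocol 10.6.6.1.3 item 3 covers a de-escalation to a level already judged safe where Part B1 participants have since been enrolled: "these participants will now be included in further dose-escalation decisions following mTPI-2 rules". This can arise because Protocol 10.6.7 states "Expansions may start before the MTD/HPDD has been determined". The text introducing Table 16 makes each decision depend on the number of participants and the number of DLTs at the dose, for up to 9 participants.

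Two definitions supply those inputs, and their scope differs.

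- **The event.** Protocol 10.6.8: "Dose limiting toxicity includes event(s) which happen during the 21 days of Cycle 1 of Part A".
- **The participant.** Protocol 10.6.10: "For decisions on dose escalation, an evaluable participant is defined as a participant who has received AZD8853" and either met the infusion and 21-day safety requirements or had a DLT. No study part is named. The Synopsis likewise says dose escalation "will be based on the dose limiting toxicity (DLT) evaluable population (all enrolled participants who complete the DLT evaluation period of 21 days", and the DLT Evaluable row of SAP Table 2 (section 3.2) has no Part A limit.

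SAP 4.2.1.8 bases the MTD evaluation on the DLT-evaluable population under a heading that limits it to Part A. Protocol 10.6.6.1.3 item 7 estimates the MTD by isotonic regression on DLT rates from dose escalation. Item 4 allows that, after a Stay decision, "additional participants will be enrolled up to a maximum of 9 participants for a given dose level".

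**The concern.** Item 3 brings B1 participants into a rule that needs a numerator and a denominator. The evaluability definitions let them into the denominator. The DLT definition, as worded, keeps their toxicities out of the numerator. A B1 participant who completes 21 days with a DLT-grade event would then be handled as event-free. One who leaves early because of it would be non-evaluable, since the event is not a DLT.

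No other clause settles the matter. The DLT-like provision in 10.6.8 is discretionary, covers unlisted events or events outside the DLT period, and does not say whether such events enter the mTPI-2 count.

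At stake is a first-in-human dose decision taken just after toxicity forced a step back. Two people applying the text in good faith could read opposite decisions from the same data.

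**Working it through.** **Inputs.** From the protocol: a beta-binomial model; the decision follows the equal-length interval with the largest unit probability mass (UPM); a dose is unsafe if the posterior probability of exceeding the target is above 95% with at least 3 evaluable; Part B1 enrols up to about 20. The target, the equivalence interval and the cells of Table 16 are redacted, so there is no plan figure to reproduce. Assumed: targets of 25, 30 and 33%, half-widths of 3, 5 and 7 points (nine settings), and a Beta(1,1) prior.

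**Formula.** With y DLTs in n participants the posterior is Beta(1+y, 1+n−y). For an interval (a, b), UPM = [F(b) − F(a)]/(b − a), with F the posterior distribution function. The interval with the largest UPM gives Escalate, Stay or De-escalate.

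**Scenario.** Part A has 0/3 at the dose (Escalate in 9 of 9 settings), and 10 B1 participants have been treated there. Counting B1 in both gives y/13, with y the number of B1 events. The literal reading gives 0/13.

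Worked example at target 30% ± 5 points, showing the largest UPM in each class:

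| Data | Posterior | Below | Within 25–35% | Above | Decision |
|---|---|---|---|---|---|
| 0/13 | Beta(1,14) | 10.25 | 0.15 | 0.02 | Escalate |
| 3/13 | Beta(4,11) | 3.32 | 3.01 | 1.57 | Escalate |
| 4/13 | Beta(5,10) | 2.12 | 3.19 | 2.56 | Stay |
| 5/13 | Beta(6,9) | 1.00 | 2.48 | 3.03 | De-escalate |

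Across all nine settings:

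| B1 events of 10 | Counted in both | Literal (0/13) |
|---|---|---|
| 2 | Escalate 9 | Escalate 9 |
| 3 | Escalate 5, Stay 4 | Escalate 9 |
| 4 | Stay 7, De-escalate 2 | Escalate 9 |
| 5 | De-escalate 8, Stay 1 | Escalate 9 |

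If some B1 participants with events drop out as non-evaluable, the literal denominator is below 13. The decision is unchanged: zero events gives Escalate in every setting for every n from 3 to 23.

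**How often.** Given that the trigger has occurred with these numbers at the dose, and with true DLT rate p, the joint chance of 0/3 in Part A and at least 4/10 in B1 is (1−p)³ × P(X ≥ 4), X ~ Binomial(10, p):

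- p = 10%: 0.729 × 0.0128 = 0.009
- p = 15%: 0.614 × 0.0500 = 0.031
- p = 20%: 0.512 × 0.1209 = 0.062
- p = 30%: 0.343 × 0.3504 = 0.120

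**Table range.** Pooled n can reach about 9 + 20 = 29, against a table that stops at 9. Larger n can be computed from the stated model but is not tabulated. The text does not say whether the cap of 9 counts B1.

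**The case against.** The strongest reply is that item 3 is the specific rule and carries its own meaning: inclusion under mTPI-2 rules means inclusion in both inputs. Sections 10.6.10 and 1.1 set no Part A limit, and 10.6.8 says that a DLT includes the listed events, which is not strictly exhaustive. Section 9.4.2 names DLTs among the safety variables and adds "These variables will be collected for all participants". This stands as evidence of intent. It does not amend the definition, which still ties the event to Part A.

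The safeguards are also real. Under Protocol 9.6 the SRC reviews all adverse event and laboratory data before deciding, and SAP 4.2.1.8.1 reports the DLTs that the SRC approved. Four or five serious toxicities in ten participants would be seen. A level closed as unacceptably toxic could not be reopened by a later Escalate. The SRC charter, which is not among the documents, may hold a working rule. None of this states how B1 events are counted.

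The trigger is narrow: B1 must open early, a de-escalation must follow, and the SRC must choose that level over an intermediate one. With two B1 events or fewer out of ten, the readings agree.

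Three stronger readings are tempting but unsupported.

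- A reader might infer that B1 toxicities would be ignored. The documents show an unreconciled definition, not that intent.
- A reader might cite the endpoint "Incidence of DLTs in dose escalation parts only" in Protocol section 3, or the Part A limits in SAP Table 4 and SAP 4.2.1.2.1, as proof that B1 events are barred from decisions. Those passages govern what is reported, not what the SRC counts.
- A reader might argue that event-free B1 participants dilute the DLT rate, by comparing with a decision that leaves B1 out. Item 3 rules out leaving them out, and event-free participants counted in both inputs would have the same effect. That is ordinary mTPI-2 behaviour with more data.

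**Conclusion.** The inconsistency is real and should be fixed. As worded, the plan admits B1 participants to the mTPI-2 denominator but has no place for their toxicities in the DLT count. Counting them in both is the likely intent.

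The choice matters from about three B1 events in ten. At three events, 4 of 9 settings change from Escalate to Stay. At four, none escalates. At five, 8 of 9 de-escalate, while the literal reading escalates in all nine.

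These decisions rest on the assumed targets, half-widths and prior, and on 0/3 in Part A with 10 B1 participants. The probability of the trigger is not estimated. Given the trigger, four or more B1 events with 0/3 in Part A is unlikely at a low true rate (0.009 at 10%) and more plausible at a higher one (0.120 at 30%). The case for the change is a cheap correction to a safety-relevant rule, not a demonstrated hazard.

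**What to change.** Reconcile Protocol 10.6.6.1.3 item 3, 10.6.8 and 10.6.10, together with SAP Table 2, 4.2.1.8.1 and 4.2.1.8.2, so that the same participants supply both the DLT count and the denominator in every mTPI-2 decision. State whether that same set feeds the isotonic-regression MTD in item 7. Which participants are included is for the sponsor to decide; no clinical rule is proposed here.

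If B1 is included, tabulate the decisions for every n above 9 that can arise, using the stated model, and state whether the cap of 9 counts B1.

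As an editorial correction only, SAP 4.2.1.8.1 should cite CSP section 10.6.8, not 6.6.5, for the DLT definition.

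The cost is protocol and SAP wording, plus a longer pre-computed table if B1 is included. No extra participants or visits are needed: in Protocol Table 13 the Part A-only footnote marks adverse event assessments only at Cycle 2 Days 8 and 15, so the Cycle 1 assessments are the same in all parts.
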